## 4 Analysis plan

For non-inferiority confirmation, a two-sided 90% CI will be calculated for the proportion difference of the primary efficacy parameters (no pain after 3 days of therapy on Day 4 according to TSS) with further evaluation of its lower boundary limit.

A non-inferiority conclusion will be made relating to the primary parameter only which will confirm the claimed efficacy. Secondary variables (including secondary efficacy and safety parameters) will be used for the research interest. Correction for multiple comparisons is not envisaged due to the trial arms number.

Descriptive statistics will include data for all randomized patients. Descriptive statistics parameters to be calculated for the quantitative variables are listed below:

- Quantity of observations (n);
- Arithmetic mean (M);
- Standard deviation (SD);
- 95% confidence interval for the mean (95% CI);
- Minimal value (min.);
- Maximal value (max.);
- Median (Me);
- Interquartile range (IQR).

For the variables presented as qualitative and serial parameters, the absolute (n) and relative (%) incidences will be calculated for every category, as well as 95% CI (unless otherwise specified).

# 4.1.1 Descriptive statistics

Descriptive statistics for the initial data (obtained during Visit 1) for all randomized patients will be presented for the following variables:

- Age (a number of complete years as at Visit 1 date based on the date of birth);
- Sex, race;
- Social habits;
- Vital signs: initial systolic blood pressure, diastolic blood pressure, breathing rate, body temperature;
- Physical examination (presence/absence of deviations from the reference for organs and organ systems);
- Hematology, biochemistry;
- Electrocardiogram: presence/absence of deviations;
- Throat pain intensity according to VAS;
- TSS evaluation;
- Symptoms duration (calculated as a number of days as at Visit 1 date based on the first signs occurrence date);

- Time since the diagnostics to the therapy initiation (calculated as a number of days as at Visit 1 date based on clinical diagnostics date);
- Concomitant diseases: rate for the main organs and systems (MedDRA terms);
- Concomitant therapy: rate for the main drug groups;

Descriptive statistics for the data obtained by Visits 2 and 3 will be presented for the following variables:

- Vital signs: systolic blood pressure, diastolic blood pressure, breathing rate, body temperature;
- Physical examination (presence/absence of deviations from the reference for organs and organ systems);
- Throat pain intensity according to VAS;
- TSS evaluation;
- Evaluation of therapy efficacy;
- Hematology, biochemistry;
- 12-lead ECG;
- Global evaluation of treatment tolerability;
- Compliance evaluation;

All the AEs and SAEs registered during the trial will be classified according to MedDRA terms. A percantage of patients with the registered AEs with relevant codes (according to MedDRA terms and term groups) will be presented for every trial arm. In addition, AEs will be classified for severity and relationship with the study drug/comparator drug.

Descriptive statistics will be presented for all parameters for each group separately.

# 4.1.2 Primary endpoint

The primary endpoint of the trial (absence of the sore throat after 3 days of therapy on Day 4) will be presented as the difference between the proportions for each arm. The group comparison will be carried out using the Fisher's exact test (one-sided test, in connection with the null hypothesis of non-inferiority). For the proportion difference, the 90% confidence interval (CI) will be calculated according to the procedure described in Newcombe, Robert G. "Interval Estimation for the Difference Between Independent Proportions: Comparison of Eleven Methods," Statistics in Medicine, 17, 873-890 (1998).

Thus, the non-inferiority will be confirmed if the limit of the two-sided 90% confidence interval for the difference in the proportions will be 14.5% or lower.

A primary endpoint analysis will be conducted both for the ITT (main analysis) and PP populations (additional analysis).

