#### **Confidence Intervals of Difference (P1-P2)**

Interval	Estimated	Confidence	Confidence
Method	Value	Limit	Limit
Chi-Square (Pearson)	0.2561	0.1456	0.3666

(The calculation results are presented in the language of the original source, i.e., from NCSS 8 statistical program).

- This is a non-inferiority trial; therefore, a non-inferiority margin for the primary endpoint should be justified and amount to not more than 14.5%.
- An expected rate of positive response to therapy (absence of a sore throat as an efficacy measure) in a comparator drug arm is 63%.
- An expected rate of positive response to therapy (absence of a sore throat as an efficacy measure) in a study drug arm is 65% (chosen within the tested hypothesis and based on the sample size and expected positive response).
- A one-sided type I error ( $\alpha$ ) = 2.5 % (0.025)
- A type II error ( $\beta$ ) = 20% (0.2), which corresponds to 80% power.
- Expected discontinuation from the trial will amount to 10% during the treatment.

The tested hypotheses are worded as follows:

1. Null hypothesis (Ho): Difference in the primary endpoint achievement incidence while using Angal, the study drug, and ANTI-ANGIN® FORMULA, the original drug, for treatment of acute infectious and

inflammatory pharyngeal diseases will exceed 14.5% in favor of ANTI-ANGIN  $^{\circledast}$  FORMULA:

$$H_0: p_1 - p_2 \le -0.145$$

2. Alternative hypothesis (HA): Difference in the primary endpoint achievement incidence while using Angal, the study drug, and ANTI-ANGIN® FORMULA, the original drug, for treatment of acute infectious and inflammatory pharyngeal diseases will not exceed 14.5% in favor of ANTI-ANGIN® FORMULA

$$H_A: p_1 - p_2 > -0.145$$

Where p1 and p2 is the primary endpoint achievement incidence while using Angal, the study drug, and ANTI-ANGIN® FORMULA, the original drug, respectively.

To calculate a sample size in every group, one can use a formula presented by Chow S, Shao J, Wang H. 2008. Sample Size Calculations in Clinical Research. 2nd Ed. Chapman & Hall/CRC Biostatistics Series. page 90:

$$n = (p_1 \times (1 - p_2) + p_2 \times (1 - p_2)) \times \left(\frac{z_{1-\alpha} + z_{1-\beta}}{p_1 - p_2 - \delta}\right)^2$$

where:

- n = Size of one group;
- z = Normal distribution function at the set levels of  $\alpha$  and  $\beta$ ;
- $\delta$  = Non-inferiority margin;
- p1 = Expected proportion in Angal group;

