# 2. Trial endpoints

# 2.1 Primary endpoint

The primary outcome measure was the percentage of patients without a sore throat after 3 days of therapy on Day 4, as evaluated by the Investigator according to the Tonsillopharyngitis Severity Score (TSS), in both Angal and ANTI-ANGIN® FORMULA arms.

TSS, a questionnaire (point scale) for healthcare professionals, is used in clinical practice as well as clinical trials to evaluate dynamic changes of symptoms severity of the infection-inflammatory process in the throat (Bereznoy VV, Riley DS, Wassmer G, Heger M. Efficacy of extract of Pelargonium sidoides in children with acute non-group A beta-hemolytic streptococcus tonsillopharyngitis: a randomized, double-blind, placebo-controlled trial). One of such clinical trials with TSS questionnaire was conducted in 2005 in Germany, ©CRO Applertee AG. A version of TSS ©CRO Applertee AG was adapted for this protocol.

TSS (Tonsillopharyngitis Severity Score) is a questionnaire for evaluation of the following symptoms severity: pharyngalgia, difficulty in swallowing, salivation, hyperemia of pharyngeal mucosa, and body temperature increase according to a 4-point scale:

- 0 = no symptom;
- 1 = insignificant symptom;
- 2 = moderate symptom;
- 3 = significant symptom.

The axillary body temperature increase is rated as follows:

- 0 points: <37.5 °C;
- 1 point: 37.5 to <38.5 °C;
- 2 points: 38.5 to <39.5 °C;
- 3 points:  $\geq$  39.5 °C.

TSS is filled in by the Investigator based on the patient complaints and physical examination data. The Investigator summarises the points obtained for every symptom to obtain a total sum of TSS points. A total sum of TSS points will be evaluated at screening to define the inclusion criteria and evaluate for the baseline level; measure efficacy of the therapy conducted in the both arms at Visit 2 (Day 4); as well as evaluate the disease outcome at Visit 2 (Day 4) and/or Visit 3 (Day 5), if applicable.

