## 3.10 Significance level

All statistical analyses in this trial will be conducted at 95% significance level (a threshold p value for confirmation of statistical significance is below 0.05), except for the primary endpoint where a one-sided statistical criterion will be used with 95% significance level (a threshold p value is below 0.05). The two-sided statistical criteria will be used for all other parameters.

For the primary endpoint evaluation, 90% CI will be calculated for the proportions difference with further evaluation of its lower boundary limit.

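### The primary risk difference is valid but unadjusted; pre-specifying adjustment for the baseline sore-throat score would probably sharpen it modestly, at little cost

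*SAP*

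**What the plan says.** The primary endpoint is the proportion of patients with no sore throat on Day 4, as scored by the investigator on the sore-throat item of the TSS. Under SAP 4.1.2 it "will be presented as the difference between the proportions for each arm". On the interval, the same section says: "For the proportion difference, the 90% confidence interval (CI) will be calculated according to the procedure described in Newcombe". It adds a one-sided Fisher's exact test. Protocol 9.1.2 gives the same analysis. Neither document names a covariate or stratum for it. SAP 3.4 and 3.5 plan no subgroup or by-site analysis, and Protocol 4.3.1 names no stratification factor for the envelope randomization.

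The baseline value exists. Protocol 4.2.4.1 lists completion of the TSS before randomization at Visit 1, and the form in Protocol Appendix 2 has a baseline entry for sore throat as a separate item. SAP 2.1 gives a baseline role only to the total score: "A total sum of TSS points will be evaluated at screening to define the inclusion criteria and evaluate for the baseline level". SAP 4.1.1 and the Table 18 template summarise the TSS descriptively. Protocol 9.1.1 tests baseline data between arms for comparability, but neither document says what follows if severity differs.

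The two documents use different error rates. Protocol 9.2 sizes the trial at a one-sided 2.5%. SAP 3.10 says that "a one-sided statistical criterion will be used with 95% significance level (a threshold p value is below 0.05", which matches the 90% interval.

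**The concern.** The endpoint is the Day 4 value of an item whose Day 1 value is known. Severe throat pain is plausibly less likely to have gone after three days than moderate pain. If so, a crude comparison leaves explainable variance in the interval and lets a chance difference in severity between arms pass into the estimate. Nothing in the randomization balances severity.

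There is also a procedural side. The plan tests for baseline imbalance without a rule for acting on it. In an open-label non-inferiority trial, that invites an argument about adjustment after the results are known. Naming the covariate beforehand settles it, whatever the precision gain.

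**Working it through.** **Inputs.** From Protocol 9.2: expected response 63% (comparator) and 65% (study drug), margin 14.5 points, one-sided alpha 2.5%, power 80%, 128 completers per arm, 140 randomized per arm, 10% loss. From SAP 3.10 and 4.1.2: one-sided 5% through a 90% interval. From the earlier placebo-controlled trial tabulated in Protocol 9.2, product arm: 2.8% mild, 72.6% moderate and 24.5% severe at baseline. The gap g in Day 4 response, non-severe minus severe, is **assumed**, because that table gives only marginal distributions.

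**The plan's own figure.** Variance sum V = 0.63×0.37 + 0.65×0.35 = 0.4606. Distance to the margin = 0.02 + 0.145 = 0.165. Then n = 0.4606 × (1.960 + 0.842)² / 0.165² = 132.8, so 133 per arm against the stated 128. The formula as printed, with p1×(1−p2) in its first term, gives 137. Exact power of the Newcombe limit at one-sided 2.5% is 79.2% at 128 per arm and first reaches 80% at 131. The software check in Protocol 9.2 used 1,000 simulations (Monte Carlo standard error √(0.8×0.2/1000), about 1.3 points), so 128 is compatible with an unadjusted analysis. The planned size does not rely on adjustment.

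**Gain from stratifying, 128 per arm.** Two strata, severe share w = 0.245, same gap g in both arms. The within-stratum variance sum is V − 2w(1−w)g² = 0.4606 − 0.370g². The half-width is 1.645 × √(variance sum/128), and power is Φ(0.165/SE − z).

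| Assumed gap g | 90% half-width (points) | Narrowing | Power, one-sided 2.5% | Power, one-sided 5% |
|---|---|---|---|---|
| 0 | 9.87 | 0% | 78.5% | 86.6% |
| 10 points | 9.83 | 0.4% | 78.9% | 86.8% |
| 20 points | 9.71 | 1.6% | 79.8% | 87.5% |
| 30 points | 9.50 | 3.7% | 81.5% | 88.7% |
| 40 points | 9.21 | 6.6% | 83.8% | 90.3% |

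These figures ignore the small price of estimating within strata. Simulating the Mantel-Haenszel difference with no association, the standard error rises from 0.0597 to between 0.0599 and 0.0600 (0.3% to 0.5%), and the stratified one is the smaller in only 26–30% of trials. At a 10-point gap, gain and price are therefore of similar size.

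**Power at the number expected to be analysed.** 140 × 0.9 = 126 per arm, and SAP 3.6 does not impute in the main analysis. SE = √(0.4606/126) = 0.0605. Crude power is Φ(0.165/0.0605 − 1.96) = 77.9% at one-sided 2.5% and Φ(0.165/0.0605 − 1.645) = 86.1% at 5%.

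With 25% severe, the variance explained is R² = w(1−w)g²/[p(1−p)], and SE is multiplied by √(1−R²):
- 45% v 68% (g = 23 points, p = 62.25%): R² = 0.1875×0.0529/0.235 = 0.042. Power is 79.6% at 2.5% and 87.4% at 5%.
- 40% v 70% (g = 30 points, p = 62.5%): R² = 0.1875×0.09/0.234 = 0.072. Power is 80.9% at 2.5% and 88.3% at 5%.

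**Chance imbalance.** The between-arm difference in the severe fraction has SD √(2×0.245×0.755/126) = 5.4 points. A 2-SD imbalance is 10.8 points. Multiplied by g of 10, 20 or 30 points, it shifts the crude difference by about 1.1, 2.2 or 3.3 points, against a margin of 14.5.

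**The case against.** The strongest case against is that nothing is wrong here. The crude difference is unbiased under randomization, it matches the unstratified allocation and the unadjusted sample-size calculation, and its interval already allows for chance imbalance. All of that stands, so a reader who infers an analysis error or bias is going further than the documents allow.

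A second objection is that the gain is unproven. That stands as well. A reader might infer that adjustment must tighten the interval at no cost, but neither document links baseline severity to Day 4 response. If severity is not prognostic, the interval is on average very slightly wider.

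Third, the power shortfall that adjustment might seem to repair exists only at the sizing alpha. Under the SAP's one-sided 5%, crude power at 126 per arm is already 86.1%. The conflict between the two alphas is a separate matter, and it moves power by 86.1 − 77.9 = 8.2 points, more than this adjustment would at any gap shown above.

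Fourth, a 0–2 v 3 split handles imbalance only across that cut, so adjustment reduces the effect of imbalance and does not remove it.

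Finally, SAP section 1 envisages no departures from the protocol, so the change takes more than one sentence in the SAP. Protocol 9.6 does, however, allow a justified deviation listed in a SAP developed before the final analysis.

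These objections limit the point without defeating it. The covariate is measured before randomization and already collected, and adjusting for it keeps the risk-difference scale and the margin.

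**Conclusion.** This is an optional improvement to a valid analysis. Pre-specified adjustment for the baseline sore-throat item would probably tighten the primary interval a little: by roughly 1.6% to 3.7% if the response gap is 20 to 30 points, by next to nothing at 10 points or less, with a loss of up to about 0.5% in standard error if there is no association. The power gain at gaps of 23 to 30 points is 1.7 to 3.0 points at one-sided 2.5% and 1.3 to 2.2 points at one-sided 5%. It would also reduce the influence of chance imbalance in severity and settle the adjustment question in advance.

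The sizes rest on three assumptions: the gap itself, a severe share near 25% as in the earlier trial, and a similar gap in both arms. The finding that the baseline item is available and unused in the primary analysis needs none of them.

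**What to change.** Before the analysis, state in SAP 4.1.2, and align in Protocol 9.1.2, that the primary risk difference is estimated with Mantel-Haenszel weights and a stratified Newcombe interval over the Visit 1 sore-throat score, 0–2 v 3, with the same margin and confidence level. Fix the two-level split in advance: with 2.8% mild, a separate mild stratum would hold about 126 × 0.028 = 3.5 patients per arm, while the severe stratum would hold about 126 × 0.245 = 31. Keep the crude Newcombe difference as a supportive analysis, and say that the Fisher test, which is also unstratified, belongs with it.

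No new data are needed. The cost is a listed and justified SAP deviation (Protocol 9.6) or a protocol amendment, which Protocol 11.2 would class as significant if it may influence the statistical methods, plus a negligible loss of precision if severity turns out not to be prognostic.

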## 4.1.3 Secondary endpoints

The following statistical analysis methods are stipulated for the secondary efficacy endpoints:

- The frequency of  $\geq$ 50% total score reduction by the TSS questionnaire completed by the Investigator relative to baseline in both Angal and ANTI-ANGIN® FORMULA arms at Visit 2 (Day 4)—the response frequencies will be compared in each time point using the Fisher's exact test.
- Total score reduction by the TSS questionnaire, as well as reduction in symptoms (sore throat, difficulty in swallowing, salivation, erythema and fever) after 3-day therapy, at Visit 2 (Day 4), relative to baseline total score—the between-arm comparison will be carried out using the Mann–Whitney test due to non-symmetrical nature of the scores distribution in the TSS scale.
- A period of time required for the symptoms resolution defined by the patient's diary (subjective patient's evaluation), but not more than 5 days within the trial (for patients who achieved the relevant outcome)—the between-arm comparison will be carried out using t-test or the Mann–Whitney test depending on the distribution character. The survival will not be evaluated due to low duration of the trial.
- The proportion (%) of patients who fully recovered on Day 4 in Group A and on Day 5 in Group B (disease outcome according to the objective evaluation by the Investigator, the total score by the TSS questionnaire  $\leq 2$ )—the between-arm comparison will be carried out using the Fisher's exact test.
- A change in the sore throat intensity by 100 mm VAS (visual analogue scale filled in by the patient) at the beginning, after 3 days of therapy, and at the end of treatment in both groups—the between-arm comparison will be carried out using the t-test.

A secondary endpoint analysis will be conducted both for the ITT (main analysis) and PP populations (additional analysis).

A multifactorial analysis of the secondary endpoints is not envisaged.

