# 3.8 Acceptable deadlines for visits and a scope of investigations

The data obtained at Visit 1 (Day 1) will be considered to be the initial data for the endpoint analysis.

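### TSS reductions are compared by an unadjusted Mann–Whitney test on change; adjusting for the collected Visit 1 score would usually sharpen these supportive results, by an amount the documents do not determine

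*SAP*

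**What the plan says.** SAP 4.1.3 names the endpoint as "Total score reduction by the TSS questionnaire, as well as reduction in symptoms" at Visit 2 (Day 4) against baseline, and states that "the between-arm comparison will be carried out using the Mann–Whitney test due to non-symmetrical nature of the scores distribution in the TSS scale". Protocol 9.1.3 says the same. Neither section puts the Visit 1 score into the comparison, and SAP 4.1.3 closes with "A multifactorial analysis of the secondary endpoints is not envisaged".

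The baseline is available. TSS is scored for every patient at Visit 1, and SAP 3.8 says "The data obtained at Visit 1 (Day 1) will be considered to be the initial data for the endpoint analysis".

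On error rates, SAP 3.10 sets "a threshold p value for confirmation of statistical significance is below 0.05" and adds "The two-sided statistical criteria will be used for all other parameters". On the role of these endpoints, SAP 4 ties the non-inferiority conclusion to the primary parameter alone and says "Secondary variables (including secondary efficacy and safety parameters) will be used for the research interest".

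SAP 4.1.3 names tests only. It plans no between-arm estimate with a confidence interval for TSS reduction, and the Table 18 shell holds counts per score and a p row.

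**The concern.** A reduction cannot exceed the score a patient starts with. Entry requires a total of at least 5, so a patient who enters at 5 and is fully cured falls by 5, while one who enters at 9 and is fully cured falls by 9. Day 4 scores are likely to crowd the floor: in the placebo-controlled trial used in Protocol 9.2, 62.5% of the product arm had no sore throat on Day 4. Ranking raw reductions therefore turns spread in entry severity into noise. The rank test deals with the skewed scores that the SAP cites, but it does not remove that noise.

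Two things are at stake: some sensitivity in the TSS comparisons, and the fact that a chance difference between arms in entry severity feeds into the result. In a non-inferiority trial, a non-significant p value from a less sensitive test, shown without an interval, is easily misread as similarity.

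**Working it through.** **The plan's own figure.** The only power or sample-size figure in the documents is 128 evaluable patients per arm for the primary endpoint (65% v 63%, margin 14.5 points, one-sided 0.025, 80% power; Protocol 9.2). Exact binomial power at 128 per arm with a Newcombe lower limit is 79.2%, so it reproduces to within a point. Neither document gives such a figure for TSS reduction. Only the 128 is used below.

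**Inputs.**
- From the documents: 128 per arm; two-sided 0.05; sore-throat scores 0/1/2/3 in the product arm of Protocol 9.2, Table 2. Counts are 0/3/77/26 at baseline (mean 2.22, SD 0.48) and 65/27/11/1 on Day 4 (mean 0.50, SD 0.72).
- Assumed: baseline/Day 4 correlation r from 0 to 0.8; 80% power for the change analysis; equal SDs for the total.

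**Formulas.** With s_b and s_f the SDs at Visit 1 and Day 4:
- V_change = s_b² + s_f² − 2·r·s_b·s_f
- V_adj = s_f²·(1 − r²)
- adjusted power = Φ((1.960 + 0.842)·√(V_change/V_adj) − 1.960)

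With equal SDs, V_adj/V_change = (1 + r)/2. At r = 0.5 this is 0.75, and 2.802/√0.75 − 1.960 = 1.275, so power is 89.9%, a gain of 9.9 points.

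For the sore-throat item at r = 0.3 (unrounded SDs 0.476 and 0.721), V_change = 0.2265 + 0.5192 − 0.2058 = 0.540 and V_adj = 0.5192 × 0.91 = 0.472. Then 2.802 × √(0.540/0.472) − 1.960 ≈ 1.03, so power is 85.0%, a gain of 5.0 points.

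| r | gain, equal SDs (points) | gain, sore-throat SDs (points) |
|---|---|---|
| 0 | 17.7 | 11.9 |
| 0.1 | 16.5 | 9.5 |
| 0.2 | 15.1 | 7.2 |
| 0.3 | 13.5 | 5.0 |
| 0.4 | 11.8 | 3.0 |
| 0.5 | 9.9 | 1.3 |
| 0.6 | 7.9 | 0.2 |
| 0.7 | 6.0 | 0.1 |
| 0.8 | 4.0 | 2.0 |

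The SD ratio matters as much as r. If the entry SD is 0.8 of the Day 4 SD, the gain runs from 12.9 points (r = 0.1) to 0.8 (r = 0.7). If it is 1.25 times, it runs from 19.0 to 14.3.

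**Check on bounded ordinal scores.** The formulas are for means, so Mann–Whitney on change was compared with rank ANCOVA of the Day 4 score by simulation (128 per arm, 1,200 trials per setting, Monte Carlo error about 1 point). The total had entry ≥5 and assumed item distributions, giving SDs of about 1.8 and 2.0. The sore-throat item used the documents' distributions.

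| score | observed r | Mann–Whitney on change | rank ANCOVA | gain (points) |
|---|---|---|---|---|
| Total | 0 | 78.8% | 96.5% | 17.7 |
| Total | 0.13 | 80.2% | 93.4% | 13.2 |
| Total | 0.28 | 76.7% | 89.6% | 12.9 |
| Total | 0.45 | 78.1% | 84.8% | 6.7 |
| Total | 0.65 | 76.8% | 80.3% | 3.5 |
| Sore throat | 0 | 82.2% | 92.8% | 10.6 |
| Sore throat | 0.14 | 79.8% | 87.2% | 7.4 |
| Sore throat | 0.27 | 79.8% | 83.8% | 4.0 |
| Sore throat | 0.42 | 78.2% | 79.4% | 1.2 |
| Sore throat | 0.59 | 80.7% | 82.3% | 1.6 |

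A second simulation of the total, with one fixed true effect and other assumed settings (1,500 trials each), gave 68% v 86% at r = 0.14, 71% v 84% at 0.26, 81% v 90% at 0.37 and 93% v 94% at 0.54. The last gain is only 1 point, partly because 93% leaves little room; the variance ratio there was still 0.84.

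**Chance imbalance.** For the sore-throat item at r = 0.3, the slope of Day 4 on Visit 1 is 0.3 × 0.721/0.476 = 0.45. Each point of entry imbalance therefore moves the change-score difference by 1 − 0.45 = 0.55. One standard error of entry imbalance is 0.476 × √(2/128) = 0.06 points, which shifts the result by about 0.03. The standard error of that result is √(0.540 × 2/128) = 0.09.

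**Fever.** Inclusion criterion 6 requires a temperature below 37.5 °C, and the TSS scores that as 0. Every eligible patient starts at 0 on this item, so no reduction can occur and a baseline term would be constant.

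**The case against.** The other side is strong on importance. Under randomisation an unadjusted rank test on change is valid, and the SAP gives its reason for choosing it and expressly declines multifactorial modelling. The endpoints are supportive and unpowered, and power to detect a difference does not itself establish non-inferiority. Baseline is partly handled elsewhere: the ≥50% reduction endpoint is scaled to each patient's entry score, recovery (total ≤2) is a level and not a change, Protocol 9.1.1 compares baseline data between arms, and Table 18 shows item scores by visit. All of this stands. It makes the point an improvement and not an error. It does not remove the inefficiency in the comparison of reductions, and seeing an imbalance at baseline does not adjust for it.

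Three stronger readings are tempting and are not supported:
- A reader might infer that the planned test loses a definite 8 to 17 points of power. That range needs equal SDs, 80% starting power and r between about 0.1 and 0.6, none of which the documents give. It is too high for the sore-throat item over most correlations and does not apply to fever.
- A reader might infer that these comparisons are the main support for the primary result. SAP 4 says otherwise.
- A reader might infer that each item's reduction is to be measured against the baseline total, which would make no sense for a 0–3 item. In this translated sentence the reference to the baseline total can attach to the total-score reduction alone. At most it needs a clarifying word.

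**Conclusion.** The point holds as a matter of precision. The planned analysis is valid but usually less efficient than one using the Visit 1 score already collected, and it carries chance entry imbalance into the between-arm result. That imbalance averages out over randomisations, so it is not bias.

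The size is conditional. From about 80% power and near-equal SDs, the gain for the total is roughly 4 to 18 points for correlations from 0.8 down to 0, with one simulated setting showing about 1 point at 0.54. For the sore-throat item it is about 0 to 12 points, and under about 5 once the correlation exceeds 0.3. For fever there is no gain. The SD ratio and correlation of total TSS are unknown, and a smaller entry SD than assumed would shrink the gain for the total.

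Nothing here touches the primary non-inferiority conclusion.

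**What to change.** In SAP 4.1.3 and Protocol 9.1.3:
- **Total TSS:** analyse the Day 4 total by rank ANCOVA, or a proportional-odds model, with arm and Visit 1 total. Name one model in advance. Report the adjusted effect with a 95% CI and keep Mann–Whitney on reduction as supportive.
- **Sore throat, swallowing, salivation, erythema:** use the Day 4 item score with arm and the same item's Visit 1 score.
- **Fever:** compare the Day 4 score between arms without a baseline term.
- Except these models from the sentence ruling out multifactorial analysis, and add the estimate and interval to the table shells.

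The cost is one more model for each score and a few lines of R, with no new data or patients. The return is small if the baseline/Day 4 correlation is high. The SAP introduction says it makes no changes from the protocol, so that statement must be revised if only the SAP is altered; Protocol 9.6 allows such a deviation to be listed and justified in a SAP written before the final analysis and described in the final report.
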